#### 4.4.2. Predictors and covariates

The primary predictor is study group, i.e. Pharmacist Care or AFM Pool Care. Covariates are other variables that could potentially mediate, moderate, or confound the association between the primary predictor and the outcomes. In this study, covariates include patient age, sex, race, ethnicity, language spoken, and comorbidities, as well as the patient's neighborhood-level SES.

#### 4.5. Data collection.

The primary outcome will be measured only among patients who have common potential drugdrug interactions (DDIs) based on a pre-specified list of medications. The outcome will be whether or not they received relevant counseling for any of their DDIs. Eligible patients in both groups will be selected using computerized pharmacy codes generated based on the protocol used by the regional pharmacy team. The computerized pharmacy codes will be used to identify patients with any of these potential DDIs in a consistent way in the Pharmacist Care and AFM Pool Care groups.

Research assistants blinded to group assignment will review text extracts from the EHR using a structured protocol to identify whether there is documentation that the patient received counseling regarding a DDI. With each study group, a random sample of eligible patients will be identified; the sample will be stratified by facility to yield a representative sample. Masking of group assignment will be conducted by one research assistant prior to review by a different

research assistant. A patient with any potential DDI will be counted as having received relevant counseling if any counseling (for any potential DDI) was documented in the text extra prior to or coincident with a Paxlovid prescription, or in the absence of a Paxlovid prescription, occurring within 2 days after the e-visit.

For the secondary outcomes, we will use data available from KPNC computerized sources, including HealthConnect (HC, aka EPIC) EHR data (from Clarity) and EPIC access logs. EHR data will be used to identify all e-visits for Paxlovid during the study period. For each patient who made an e-visit, the EPIC access log data for the subsequent 5-day period will be analyzed to identify how many minutes of pharmacist or physician time were associated with that request.

For the exploratory outcomes, patient care experience will be evaluated by surveying a sample of patients selected at random in the service areas in the Pharmacist Care and AFM Pool Care groups. We have designed a short survey that takes no more than 5 to 10 minutes to complete. The survey will be fielded by email, mail, and telephone. Due to the fact that we are asking about a specific care experience and patients' recall fades quickly after 2 weeks, we will field the survey using all 3 modes in a relatively efficient sequence. A letter containing a description of the study, language regarding informed consent and confidentiality, and the survey will be sent by mail on day 11 after the e-visit, and an email with a link to the online version will be sent on day 14. Telephone administration will be attempted (up to 4 attempts total) starting on day 17 for those who have not replied to the paper or online survey. A small gift to thank patients for considering participation will be included in the mailing. Responses will be treated as confidential and data will be aggregated, with no individual identifiers associated with data presented in reports.

Patient-reported outcomes will be reported on a 5-point scale and will include:

- a. Satisfaction with the overall quality of care
- b. Satisfaction with the timeliness of care
- c. Confidence in the care provided

Clinician satisfaction with the process of care will be evaluated by surveying all pharmacists on the regional team providing Pharmacist Care, plus the AFM site leads for Paxlovid e-visits in the service areas participating in the study. Because the AFMs in each service area cross-cover the Paxlovid e-visit requests from all facilities in that service area, it will not be possible to survey front-line AFMs in the two groups separately, and it would not be productive to ask the AFMs about their experience with Pharmacist Care because they would typically only have direct experience with Pharmacist Care if a problem arose that required their attention.

The pharmacist and physician surveys have been designed to require no more than 3 to 5 minutes to complete. These surveys will be fielded via Outlook email using a Teams form, as well as on paper via interoffice mail. A small gift to thank pharmacists and physicians for considering participation will be included in the mailing. Responses will be treated as confidential and data will be aggregated, with no individual identifiers associated with data presented in reports.

Data collected from both pharmacists AFMs and will include:

- a. Satisfaction with the process of care (on a 5-point scale)
- b. Suggestions for improving the care process (open-ended)

4.6. Statistical analysis plan.

During the survey and visit review components of this study, it became clear that more patients than projected had received pharmacist care. A preliminary analysis conducted on 12/18/2024, prior to evaluating any outcomes, found that the facility assigned to each e-visit usually did \*not\* match the home facility of the patient who initiated the e-visit. This was most likely due to an operational workflow (which is still being elucidated) that was unanticipated at the time this study was designed and facilities were assigned at random to the Pharmacist Care vs. Physician Care groups. Due to the fact that the patient's "home" facility became imbalanced, we will include this as a covariate in the primary analysis (see below).

The primary analysis will group each patient based on which type of clinician (pharmacist or physician) first accessed the eVisit. This is similar to a per-protocol analysis. A patient whose eVisit was first accessed by a pharmacist will be counted in the pharmacist group, even if the eVisit was referred to a physician. A patient whose eVisit was first accessed by a physician will be included in the physician group, even if the eVisit was referred to a physician group, even if the eVisit was referred to a physician group, even if the eVisit was referred to a pharmacist. We select this approach as the primary analysis because it best reflects what patients experience in real-life care delivery, which this study is intended to evaluate.

A secondary analysis will treat each patient as part of the group to which they were assigned based on the facility listed on the e-visit worklist (intention-to-treat). However, this approach may be worse at reflecting the actual patient experience because dozens of pharmacists and physicians were involved in executing the randomization assignments. It is possible that some patients will have received a different mode of care from the group to which they were assigned.

The primary outcome is binary, i.e., whether or not a patient received counseling for a DDI. This will be compared between study groups using mixed effects logistic regression providing point and interval estimates of outcome odds ratios associated with study group. This analysis technique accounts for the within-facility correlation among patients to obtain valid estimates of treatment effects and associated standard errors. The pre-specified set of covariates for inclusion in regression models include: study group and covariates used in the randomization procedure (i.e. patient socioeconomic status (using the Neighborhood Deprivation Index), patient race/ethnicity, and service area level COVID-19 incidence). Study group and other covariates will be treated as fixed effects and the patient's home facility and e-visit facility will be handled as random effects.

In addition, exploratory/sensitivity analyses will examine the impact of including additional covariates in our estimation of treatment effect, with focus on variables with chance imbalance in distributions by treatment group, as determined in preliminary analyses. Analyses resulting in an appreciable change in the estimate of treatment differences or increased precision of the treatment effect will be noted.

For the secondary outcomes, we will compare the estimated cost per Paxlovid message, the minutes spent per message, and the hours from e-visit to prescription order between the Pharmacist Care and AFM Pool Care groups using linear mixed regression models, providing point and interval estimates of between-group differences in mean outcomes. If cost or minutes have a skewed distribution, log transformation will be used. Analyses of other secondary outcomes with that are continuous will be similar. The approach to inclusion of covariates and sensitivity/exploratory analyses is as described for Aim 1.

Patient satisfaction and other care experience scores will be compared between the study groups using linear mixed effects regression with log transformation if needed for skewed data, with analyses paralleling that described for the other secondary outcomes.

For all aims, secondary analyses will assess variation in the estimates of treatment effect by age, race/ethnicity/language group, and comorbidity score group (high, medium, low) via stratification by level of the potential effect modifier. These stratified analyses will inform the fitting of regression models with appropriate cross-product terms between the potential effect modifier and study group indicator variable, allowing for a more formal assessment of heterogeneity in treatment effect.

A service area or facility may drop out before completion of the study if they were assigned to AFM Pool Care but add local pharmacist management, thus diverging from their assigned group. Paxlovid e-visits from such a service area or facility will be censored as of the dropout date (the date that local pharmacist management began).

Tests of significance will be two-tailed with an alpha of .05. No Bonferroni or other formal correction for multiple comparisons will be used, but results will be interpreted with the multiple testing issue in mind.

4.8. Sample size and power. To estimate the available sample, we extrapolated from April 2023. This was a month when COVID-19 incidence was low to medium; 4900 e-visits for Paxlovid were made across the 15 KPNC service areas. Based on this, an average of 1089 e-visits occur per week during low to medium COVID-19 incidence periods. However, e-visits that need to be answered on weekend days will not be eligible for pharmacist management; all of these will be excluded from the study. If 5 out of 7 e-visits occur on weekdays, an estimated 778 e-visits occur on weekdays during times of low to medium COVID-19 incidence.

This study will include 17 facilities that serve 872,200 adult members, or 25% of the 3.55 million adult members in the region. Each week, the estimated number of e-visits eligible for study is 25% of 778, or 195. Assuming an 8-week evaluation period, the estimated sample size is 1,560, or 92 patients in each of the 17 clusters.

Given the group-randomization study design, calculation of sample sizes and minimum detectable treatment effects must account for the expected intraclass correlation (ICC) of observations within facilities. The ICCs in outcomes of interest are expected to be quite small, and therefore we present minimum detectable effects for an expected ICC of .01.

For Aim 1, the primary outcome is the % of patients with common potential DDIs who received counseling. We conservatively estimate that 70% of patients in the Pharmacist Care group will have received DDI counseling. A clinically meaningful difference between the two groups would be a relative risk (RR) of 0.8, which corresponds to a small effect size. To attain 80% power to identify such an effect with a two-tailed alpha of 0.05 and an ICC of .01, we need a sample size of 250 in each group and will plan our review of text extracts from the EHR accordingly.

For Aim 2, the example hypothesis is that the cost of management per e-visit for Paxlovid will be lower in the Pharmacist Care group than in the AFM Pool Care group. Given a two-tailed alpha of .05, the sample size of this study has 80% power to identify an effect size of 0.20 standard deviation units, which is a relatively small effect size. In other words, this study will have good power to find a statistically significant difference between the Pharmacist Care and AFM Pool Care groups even if the effect is relatively small.

For the patient survey in Aim 3, the sample size is selected to balance power and feasibility. We aim to collect completed surveys from 200 patients in each of the two study groups. We

estimate a response rate of 60%. To obtain 200 completed surveys in each group, we estimate needing to attempt surveys with 333 patients in each group. The completed sample size of 200 in each group will give us good power to identify relatively small differences in satisfaction scores, which are measured on a continuous scale. We will be able to detect effect sizes of .31 relative to a standard deviation of 1.

The purpose of the pharmacist and AFM surveys is process assessment and performance improvement. These surveys will focus on qualitative, open-ended responses; thus, sample size and power are not estimated here. We will survey all pharmacists on the regional team providing Paxlovid e-visits (estimated n=10). We also will survey the AFMs who are Paxlovid e-visit site leads (estimated n=12).

Date	Operational team	Research team
Sep 25	Pilot care delivery to the service areas to receive Pharmacist Care; run-in period	Not included in study
Oct 9	Continue care delivery at steady state	
 
Start of study period 
 
Conduct review of text extracts from the EHR (random sample throughout period)
 
Conduct patient surveys (random sample throughout period)
 
Conduct pharmacist and AFM surveys (mid-Nov. to early Dec.)
 
 
 

Dec 11	End study – pharmacists cover all service areas	End of study period
Dec 11 – Jan 12		Analyze computerized data of outcomes for Aims 1 and 2 Complete data collection with clinicians and patients
Jan 12 – Feb 2		Finish cleaning and analysis of data from clinicians and patients
Feb 2 –		Create reports for internal use Share findings with other TPMG and KFH leaders Draft manuscript for journal submission

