# 4. Approach

## 4.1. Design, setting, and participants.

This cluster randomized clinical trial will assign patient requests for Paxlovid made via e-visits to either Pharmacist Care or AFM Pool Care, which consists of management by medical centerbased pools of AFMs in adult and family medicine (AFM). The unit of randomization is the KPNC facility. KPNC is an integrated health care system with 4.6 million members served by more than 9,500 physicians and 87,000 employees in 15 service areas. It has a mature EHR (EPIC/HealthConnect, adopted circa 2008) and encourages members to use a wide array of options for outpatient care, including secure messages to physicians via the EHR portal, e-visits, video, telephone, and in-person office visits.

The target population is adults 18 years and older in facilities within participating KPNC service areas who submit requests for Paxlovid on weekdays during the study period using the e-visit protocol accessible via the electronic portal kp.org. Messages that are handled from 8:00 am to 4:30 pm, Monday through Friday will be included. The study period will run from October 9 to December 11, 2023. Pharmacist Care will not be available for Paxlovid e-visits that need to be reviewed on weekends or holidays. These are managed by virtualist physicians in the regional call center and will be excluded from this study.

Of KPNC's 15 service areas, 4 have not implemented pharmacist management in any facility. These service areas and their facilities are eligible for this study; others must be excluded. The eligible service areas are SCL, SJO, SRF, and SSC. These service areas contain 17 facilities; each facility will be treated as a cluster in the random assignment process.

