# 4.2. Intervention.

All procedures will be conducted as part of standard of care. In the Pharmacist Care group, each e-visit message requesting Paxlovid will be assigned to a pharmacist on the regional team. Pharmacists will review requests using a standard protocol. They will call patients via telephone to elicit additional information where needed, file Paxlovid prescriptions when appropriate, and arrange home delivery when requested.

The protocol for pharmacists has a list of common potential drug-drug interactions and provides guidance for how these should be handled. Drug-drug interactions are documented by pharmacists using a smartphrase in Epic, the electronic health record (EHR). Some DDIs may lead to changes in medications while a patient is taking Paxlovid.

In the AFM Pool Care group, each e-visit message requesting Paxlovid will be assigned to a pool of AFM physicians based at the medical centers in a given service area. Physicians will review requests using the existing standard regional protocol (as well as any existing medical center-level protocols). The regional Paxlovid E-visit User Guide illustrates how to use SmartSets to document the plan and respond to patients with the outcome (eligible, not eligible, or further discussion needed). Following this protocol, physicians call patients via telephone to elicit additional information where needed, file Paxlovid prescriptions when appropriate, and arrange home delivery when requested.

4.3. Randomization. In each of the participating service areas, facilities have been assigned at random to either the Pharmacist Care or AFM Pool Care group. We used covariate-constrained randomization, a method to prevent imbalances on important variables that may be associated with the outcomes. We conducted preliminary analyses to characterize facilities with regard to population size, socioeconomic status (using the Neighborhood Deprivation Index), race, ethnicity, and COVID-19 incidence in the service area since the start of the pandemic. We have chosen these variables for use in the restricted randomization given the expected association with study outcomes, along with the expected level of between facility variability which would increase the likelihood of between-arm imbalance. We also stratify randomization on service area for within-area balance on number of facilities assigned to the Pharmacist Care and AFM Care groups.

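### The primary analysis compares patients by which clinician type first opened the e-visit, not by the facility randomisation; the assigned-group analysis is only secondary

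*Combined protocol and SAP*

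**What the plan says.** Section 4.1: "The unit of randomization is the KPNC facility". Section 4.3 describes a covariate-constrained allocation of the 17 facilities, stratified by service area. Section 4.2 describes routing by arm. Under Pharmacist Care, "each e-visit message requesting Paxlovid will be assigned to a pharmacist on the regional team"; under AFM Pool Care, messages go to the service area's physician pool.

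Section 4.6 defines the main comparison differently: "The primary analysis will group each patient based on which type of clinician (pharmacist or physician) first accessed the eVisit". A patient stays in that group even if the e-visit is later referred to the other profession. The plan likens this to a per-protocol analysis and prefers it as closest to real-life care. The assigned-group analysis, which the plan calls intention-to-treat, is secondary and uses the facility on the e-visit worklist.

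The background is also in 4.6. During data collection "it became clear that more patients than projected had received pharmacist care". The e-visit's facility usually differed from the patient's home facility, which the plan attributes to "an operational workflow (which is still being elucidated) that was unanticipated at the time this study was designed", and home facility became imbalanced. On timing, the mismatch came from this step: "A preliminary analysis conducted on 12/18/2024, prior to evaluating any outcomes".

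The primary model adjusts for neighbourhood deprivation, race/ethnicity and area COVID-19 incidence, with random effects for home and e-visit facility. Section 4.4.2 describes covariates as "other variables that could potentially mediate, moderate, or confound the association between the primary predictor and the outcomes" and says that "covariates include patient age, sex, race, ethnicity, language spoken, and comorbidities", plus neighbourhood SES.

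**The concern.** Randomising facilities protects a comparison of patients grouped by the allocation of their facility. It does not protect a comparison grouped by an event that follows allocation, and which clinician opens the e-visit first is such an event. Patients handled by the other arm's clinicians are reclassified, not excluded, so the accurate term is as-treated. The plan's likening to per-protocol understates the departure. The between-arm balance reported in 4.3 does not carry over to groups formed by first access.

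Any difference between patients reached first by a pharmacist and those reached first by a physician can be mixed with the effect of pharmacist care. This affects the headline odds ratio for counselling on drug-drug interactions (DDIs), and the Projected Impact section says the findings will inform how pharmacists are deployed.

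**Working it through.** **1. Which groups did randomisation form?** Setting 4.1 and 4.3 beside 4.6, allocation attaches to a facility and the primary contrast attaches to the first-accessing clinician. The two coincide only if every e-visit is opened first by the arm's own clinician type. Section 4.6 accepts that some patients may have received the other mode of care and gives no rate.

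**2. What does the primary model adjust for?**

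| Covariate in 4.4.2 | In primary model (4.6)? |
|---|---|
| Neighbourhood SES | yes |
| Race, ethnicity | yes |
| Age | no |
| Sex | no |
| Language | no |
| Comorbidities | no |

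The four omitted items are patient characteristics that exist before the e-visit. Section 4.6 offers sensitivity models with added covariates, and stratified or interaction analyses by age, race/ethnicity/language and comorbidity. The first check robustness and the second examine effect modification. Neither changes the primary estimate.

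**3. The plan's own sample size (4.8).** Inputs: 70% counselled under Pharmacist Care; relative risk 0.8, so 0.70 × 0.8 = 56%; two-sided alpha 0.05; ICC 0.01; 250 per group; 17 clusters.

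- Design effect = 1 + (500/17 − 1) × 0.01 = 1.284.
- Patients per group under individual randomisation: 186, or 200 with continuity correction. Times 1.284, this is 239 or 257, which bracket the stated 250.
- Power at 250, normal approximation: SE = √[(0.70×0.30 + 0.56×0.44) × 1.284/250] = 0.0484; 0.14/0.0484 = 2.89; power = Φ(2.89 − 1.96) ≈ 82%.
- Planned odds ratio = (0.70/0.30)/(0.56/0.44) = 1.83.

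The figure reproduces, but only if assignment and care received coincide.

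**4. What would an assigned-group primary cost?** Let q be the difference between arms in the proportion receiving pharmacist care. With symmetric crossover the rates become 0.70 − 0.14(1 − q)/2 and 0.56 + 0.14(1 − q)/2. All values of q below 1 are assumed.

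| q | Rates | Odds ratio | Power |
|---|---|---|---|
| 1.0 | 70.0% vs 56.0% | 1.83 | 82% |
| 0.8 | 68.6% vs 57.4% | 1.62 | 63% |
| 0.6 | 67.2% vs 58.8% | 1.44 | 41% |
| 0.5 | 66.5% vs 59.5% | 1.35 | 30% |

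If all crossover were from AFM Pool Care to pharmacists, power would be 64%, 42% and 31% in the last three rows, so direction matters little.

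**5. What could bias do to the first-access test?** For illustration only, take no true effect, a mean counselling rate of 63%, 250 per group and the same design effect. An assumed selection difference of 3, 5, 7 or 10 points raises the two-sided rejection rate from 5% to about 9%, 18%, 30% or 53%. The documents give no basis for choosing among these.

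**The case against.** There are four good points in the plan's favour.

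- *Routing looks administrative.* Section 4.2 assigns messages to a regional team or to service-area pools, and 4.5 says physicians cross-cover all facilities in their area. A patient referred after first access is not reclassified, so clinically driven escalation, the most obvious route to confounding by indication, does not move patients between groups. This stands and limits the concern. It does not show that first access was as good as random, because the plan says the workflow is not yet understood.
- *The choice is disclosed and stated to precede outcome evaluation.* This stands. It answers suspicion of a data-driven choice, not confounding.
- *The worklist-facility analysis may not be the randomised comparison either.* This also stands. The worklist facility usually differs from the home facility for an unexplained reason, so it may itself be a product of routing after allocation. It cannot be promoted without checking.
- *Outcome measurement is even-handed.* The same pharmacy codes select DDI patients in both groups, and chart reviewers are masked (4.5). This protects against ascertainment bias, not against differences between the patients compared.

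A reader might also infer from the excess of pharmacist care that crossover ran from the physician arm to pharmacists. The documents do not support that. Section 4.6 links the excess to a mismatch between home and e-visit facility, which may arise before or at worklist assignment and need not be departure from the worklist-assigned arm.

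**Conclusion.** The concern holds as a design point: the primary contrast is as-treated and not protected by randomisation, and the comparison by assignment has been made secondary. This should be corrected before analysis, because it determines the main result.

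It does not hold as a claim that the estimate is biased. A reader might infer that sicker or more complex patients were steered to one profession; no passage says so. Confounding is possible, and its size and sign cannot be bounded, because the documents give neither a crossover rate nor patient characteristics by first access. If crossover from the assigned arm is small, the two analyses nearly coincide. If it is large, the first-access groups depart furthest from the randomised ones, and the assigned-group analysis loses the most power.

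The power figures rest on the plan's 70% and 56%, ICC 0.01, 250 per group and the assumed separations. They measure the cost of the correction, not the bias.

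**What to change.** 1. Make the analysis by randomised assignment primary. Keep the first-access comparison as supportive, labelled as-treated and non-randomised. Before outcomes are examined, establish and state which facility variable, worklist or home, carried the allocation when the e-visit was routed. Use the planned worklist-facility analysis if that facility was set independently of patient features and clinician availability. Fix the other definition in advance as a sensitivity analysis, so that neither is chosen on results.
2. Report assigned arm by clinician type at first access, and home facility by worklist facility.
3. Add age, sex, language and comorbidities to the first-access model, whichever analysis is primary.
4. State in 4.8 that 250 per group assumes no crossover.

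Cost: SAP wording, two descriptive tables, covariates the plan already lists, and an inquiry into the routing workflow that the plan says is under way. Both main analyses are already planned; the other facility definition adds one sensitivity run. The real price is dilution of the assigned-group estimate and the loss of power shown above. That loss should be disclosed; it is not a reason to let a non-randomised contrast carry the main conclusion.
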